3.3. Sample Size Considerations

A sample size of 414 subjects with 1:1 randomization (itacitinib vs placebo) and stratification based on baseline aGVHD risk status (standard risk vs high risk) provides approximately 90% power to test for the primary endpoint (ORR at Day 28) and approximately 80% power to test for the key secondary endpoint (NRM rate at Month 6). The family-wise α -level will be controlled at 0.025 overall for the two comparisons. Specifically, this study will claim to have achieved the efficacy objective when the primary endpoint ORR at Day 28 shows a significant treatment effect at 1-sided $\alpha = 0.025$. Conditional on significance of the primary endpoint, the key secondary endpoint (NRM rate at Month 6) will be tested at 1-sided $\alpha = 0.025$.

An absolute improvement of 16% in the primary endpoint of ORR at Day 28 would be considered a clinically meaningful improvement over standard first-line systemic treatment for aGVHD. A sample size of 414 subjects (207 subjects per treatment group) will provide approximately 90% power to detect a 16% overall difference (72% vs 56%) between treatment groups for the primary endpoint (ORR at Day 28) at a 1-sided alpha level of 0.025.

The assumed Day 28 ORR of 56% is based on MacMillan et al (2015). The stratum-specific response rates (standard risk, 68%; high risk, 44%) assume a standard risk:high risk ratio of 0.50:0.50. It is expected that treatment with itacitinib will result in a 16% increase in the ORR, that is, an expected odds ratio of 2.02 (which corresponds to an overall increase in ORR to 72%), with stratum-specific response rates of 81% and 61% for standard-risk and high-risk aGVHD cohorts, respectively. Power for the CMH test with stratification based on GVHD risk score was calculated using software N-Query 5.0.

[figure not shown]

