3.4. Interim and Final Analyses

There are 2 interim analyses planned in this study. Interim Analysis 1 will be conducted at the time when 112 subjects have completed the Day 28 visit or withdrawn from the study. Only a futility analysis will be conducted based on test statistic of Day 28 ORR using stratified CMH test (see details below). The observed normalized z statistic will be compared with the futility boundary of 0.626 as depicted in Figure 3 (equivalently conditional power equal to 0.2); if the normalized z statistic is less than the futility boundary, it is recommended to stop the study early for futility. Interim Analysis 2 will be conducted when approximately 240 subjects have completed the Day 180 visit or have withdrawn from the study. At Interim Analysis 2, both futility and efficacy will be tested for Day 28 ORR using stratified CMH test with z-score efficacy boundary of 2.25 and futility boundary of 1.46 corresponding to conditional power of 0.2. Critical value at final analysis is 2.02. See details on boundary specifications in Sections 3.4.1 and 3.4.2. Note that boundaries for both the Interim Analysis 2 and the Final Analysis are constructed based on a hypothetical example solely for illustration purposes, whereas the real boundaries used in the study will be based on the observed information fraction at Interim Analysis 2.

Figure 3: Upper Efficacy and Lower Futility Boundaries for Day 28 ORR at the Interim Analyses and Critical Value at the Final Analysis

In any interim analysis, the sponsor may consider stopping the study for futility if the conditional power is less than 20% and stopping for efficacy if both efficacy boundaries are crossed. If neither the efficacy nor the futility boundary for Day 28 ORR is crossed, the study will continue. Additionally, if efficacy for Day 28 ORR is crossed but efficacy for Day 180 NRM rate is not crossed, the study will continue.

3.4.1. Interim Analysis 1

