The first interim analysis for futility only will be performed when 112 subjects (25.7% of the planned 436 subjects) have completed the Day 28 visit or withdrew early from study. No alpha will be spent during the first interim analysis. The stopping rule is nonbinding. When the conditional power is < 20%, the sponsor may consider terminating the study if the totality of evidence is warranted. The conditional power is calculated assuming that the estimated treatment effect at the interim analysis is the true effect using the formula (Jennison and Turnbull 1999):

$$\Phi \left(\frac{z}{\sqrt{t(1-t)}} - \frac{z_{\alpha/2}}{\sqrt{1-t}} \right)$$

where Φ is the cumulative distribution function of the observed normalized test statistic z , and t is the information fraction (ie, observed sample at interim divided by the planned total sample size 436); $t = 0.257$ at Interim 1 and $z_{\alpha/2} = 1.96$.

Since CMH test with only 1 stratification factor, aGVHD risk status (standard vs high risk), will be used to test ORR at Day 28, it is thus a chi-square test with degree of freedom equal to 1, that is, $\chi^2_{df=1}$. Taking the square root of the observed CMH test statistic $\chi^2_{df=1}$ will result in normalized test statistic z .

3.4.2. Interim Analysis 2

For Interim Analysis 2, the analysis of both efficacy and futility will use a clinical database cutoff based on when 240 eligible subjects (55.0% of the targeted 436 subjects) have completed the Day 180 visit or withdrew from the study prior to Day 180.

The Hwang-Shih-DeCani alpha spending function with shape parameter -4 (O'Brian-Fleming like boundary) will be used to define upper efficacy boundary for the primary analysis of ORR at Day 28 when approximately 240 eligible subjects reach Day 180 (Hwang et al 1990). Based on enrollment projection, there will be approximately 360 subjects who have completed Day 28.

Table 2 lists efficacy boundary when information fraction (ie, the percentage of subjects) is 0.826 (360 subjects complete Day 28) at Interim 2; if ORR tested at Day 28 crosses the boundary, then the key secondary endpoint, 6-month NRM rate, will be tested by using the Bonferroni method for alpha spending (ie, 0.0125 as compared with 1-sided p-value at both interim and final analyses). By simulation, without considering early stopping for futility, the power of testing 6-month NRM at Interim 2 (with 240 eligible subjects who have completed Day 180) is approximately 0.608.

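### The stated 90% power for Day 28 ORR takes no account of the futility looks; if the nonbinding Interim 1 recommendation is followed, power is about 0.78 to 0.81, and the plan should give both figures

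*SAP*

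**What the plan says.** SAP 3.3 states that the sample size "provides approximately 90% power to test for the primary endpoint (ORR at Day 28"), from a two-stratum CMH calculation in N-Query. Protocol 9.2 says the same. Neither section says whether futility stopping is included.

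SAP 3.4 sets the Interim 1 rule: "The observed normalized z statistic will be compared with the futility boundary of 0.626 as depicted in Figure 3". A z below 0.626 leads to a recommendation to stop. SAP 3.4.1 explains the basis: "The conditional power is calculated assuming that the estimated treatment effect at the interim analysis is the true effect". SAP 3.4.1 and Protocol 9.2.1 call the rule nonbinding and say that the sponsor may consider stopping on the totality of evidence.

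At Interim 2, SAP 3.4 and 3.4.2 give an efficacy boundary of 2.25 and a futility boundary of 1.46, with a final critical value of 2.02. SAP 3.4 describes the Interim 2 and final boundaries as illustrative, to be recalculated from the observed information.

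The only power figure with a futility qualifier is the Interim 2 power for NRM (0.608), which is said to ignore early futility stopping. The ORR figure has no such qualifier. Neither document gives the chance of crossing 0.626 when the planned effect is true.

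**The concern.** A reader will take 90% as the power of the design as described, including its recommended stops. Making a futility rule nonbinding protects type I error; it does not protect power when the rule is followed. Interim 1 falls at about 26% of the information, with 56 subjects per arm, and extrapolates a noisy observed trend. An observed ORR difference below about 6 points triggers the recommendation, although a true 16-point difference produces such a result fairly often. At stake are the accuracy of a stated design property and how a DMC or sponsor reads a low current-trend conditional power.

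**Working it through.** **Inputs (SAP 3.3, 3.4 and Table 2).** Sample size: "A sample size of 414 subjects (207 subjects per treatment group"). Effect: "approximately 90% power to detect a 16% overall difference (72% vs 56%) between treatment groups", tested "at a 1-sided alpha level of 0.025". Control: "stratum-specific response rates (standard risk, 68%; high risk, 44%) assume a standard risk:high risk ratio of 0.50:0.50". Itacitinib: "stratum-specific response rates of 81% and 61% for standard-risk and high-risk aGVHD cohorts, respectively". Looks at t = 112/436 = 0.257, 360/436 = 0.826 and 1. Efficacy boundaries 2.24981 and 2.015483. Futility boundaries 0.626 and 1.46.

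**1. Reproduce the 90%.** With 414 subjects there are m = 103.5 per arm per stratum.
- Expected CMH numerator: (m/2) × (0.13 + 0.17) = 51.75 × 0.30 = 15.525.
- Null variance: m²/(2m − 1) × (0.745 × 0.255 + 0.525 × 0.475) = 52.00 × 0.4394 = 22.85; SD 4.780.
- Drift: 15.525/4.780 = 3.248.
- Variance under the alternative: 51.75² × (0.2176 + 0.1539 + 0.2464 + 0.2379)/103.5 = 22.14; SD 4.706.
- Power: Φ((15.525 − 1.96 × 4.780)/4.706) = Φ(1.308) = 0.905.

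At 436 subjects the drift is 3.334 and power 0.919. The stated 90% is therefore the fixed-sample figure.

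**2. Reproduce the futility boundaries.** Setting the SAP's conditional power to 0.20 gives z = √(t(1 − t)) × (1.96/√(1 − t) − 0.8416).
- t = 0.257: 0.4369 × (2.2737 − 0.8416) = 0.626.
- t = 0.826: 0.3794 × (4.6945 − 0.8416) = 1.46.

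Both match the SAP.

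**3. What 0.626 means at Interim 1.**
- Observed difference: 0.626 × √(2 × 0.64 × 0.36/56) = 0.057, about 5.7 points.
- Conditional power at that z under the planned effect: Φ((0.626√t + 3.248(1 − t) − 1.96)/√(1 − t)) = Φ((0.317 + 2.414 − 1.96)/0.862) = Φ(0.894) = 0.81. Across reasonable drifts and critical values the range is 0.80-0.83, against 0.20 on the current trend.
- Chance of crossing when the drift is set for exactly 90% power: Φ(0.626 − 3.2415 × √0.257) = Φ(−1.017) = 0.155.

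**4. Overall power.** The interim and final z-values were drawn jointly normal, with means drift × √t and correlations √(tᵢ/tⱼ) (4 million draws). A patient-level CMH simulation (400,000 trials) was run as a check.

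| Scenario | Stop at Interim 1 | Efficacy boundaries only | Interim 1 futility followed | Both futility rules followed |
|---|---|---|---|---|
| Drift for exactly 90% power | 15.5% | 0.895 | 0.787 | 0.781 |
| CMH drift, 414 | 15.0% | 0.900 | 0.794 | 0.788 |
| CMH drift, 436 | 14.0% | 0.914 | 0.812 | 0.806 |
| Patient level, 436 | 14.9% | 0.916 | 0.806 | 0.800 |
| Patient level, about 414 | 15.5% | 0.899 | 0.789 | 0.783 |

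**5. Where the loss arises (CMH drift, 414).** Interim 1 costs 0.900 − 0.794 = 0.106. So about 71% of the trials stopped there (0.106/0.150) would have gone on to succeed. Interim 2 futility then costs 0.794 − 0.788 = 0.006; applied alone it costs 0.900 − 0.889 = 0.011.

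**6. Power given that Interim 1 was passed.** 0.788/(1 − 0.150) = 0.93 at 414, and 0.806/(1 − 0.140) = 0.94 at 436.

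**7. Sign of z.** SAP 3.4.1 takes z as the square root of a chi-square, which loses the sign. Read literally as |z| < 0.626, the stop probability is 13-14% and power with the rules followed is 0.79-0.82. The conclusion does not change.

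**The case against.** The strongest reply is that nothing printed is miscalculated. The 90% is tied to a CMH calculation and is right for it, and 0.626 follows from the stated formula. The rule is nonbinding, and most of the text says only that the sponsor may consider stopping. The lower figure therefore assumes full adherence to an advisory rule. All of this stands. It limits the point to an unreported operating characteristic and means that the lower figure should not replace the 90%.

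Three stronger readings might be inferred, and the documents do not support them.

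- **That the trial as run has about 80% power.** SAP 5.3.1 dates the Interim 1 cutoff 25 JUN 2018, and SAP 5.3.2 dates the Interim 2 cutoff 17 APR 2019, so the trial continued. The Interim 1 result is not given: either the boundary was not crossed, or it was crossed and the sponsor proceeded, as the rule allows. Given passage, power under the planned effect is about 0.93.
- **That the Interim 1 boundary is an error and should be lowered.** That look is past. The choice is also a trade-off: 0.626 stops about 73% of trials with no effect, against 31-50% for boundaries between −0.5 and 0. The plan sets no maximum power loss that the rule breaches.
- **That Interim 2 futility is a material drain.** Its boundary is illustrative, and SAP Appendix D tabulates only 410-435 subjects. At 420 subjects (t = 0.963) the rule alone costs about 0.2 points (0.907 to 0.905).

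What remains is that the SAP itself recommends stopping below 0.626, attaches a futility caveat to the NRM power at Interim 2, and attaches none to the ORR power.

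**Conclusion.** The point holds as one of incomplete reporting. ORR power is about 0.90 if the nonbinding futility rules are not applied and about 0.78-0.81 if they are followed, with a 14-15% chance of stopping at Interim 1 under the planned effect. The loss is roughly 10-11 points, almost all from Interim 1. Type I error is not inflated.

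The figures rest on the planned stratum rates, a 50:50 risk mix, full adherence to the recommendations, and the illustrative Interim 2 timing. They take 414 to 436 subjects as assessed. If 5% of 436 are missing and counted as nonresponders, the two figures fall to about 0.87-0.88 and 0.75-0.76, with a similar gap.

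**What to change.** In Protocol 9.2 and SAP 3.3, state both ORR power figures: about 0.90 without futility stopping, and about 0.78-0.81 with the nonbinding rules followed. Label them as pre-trial design operating characteristics. Add that power given passage of Interim 1 is about 0.93, so that the lower figure is not read as the power of the continuing trial. The Protocol synopsis repeats the 90% and should agree.

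For any futility assessment still to be made, give the DMC conditional power under the planned effect (72% vs 56%) beside the current-trend value. No change to the Interim 1 boundary is proposed.

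The cost is a few sentences and one extra line in the DMC output. Boundaries, alpha, sample size and conduct are unaffected; the stated power simply reads less favourably.

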Table 2: Operation Characteristics Using Hwang-Shih-DeCani Alpha Spending Function With Shape Parameter -4

		No. of Subjects (%)	Alpha Spent /Cumulative	Efficacy Boundary or Critical Value (as Compared With Observed Normalized Test Statistic z)	Nominal Significance /Alpha Level: $1 - \Phi(d)$	Efficacy Boundary or Critical Value at Chi-Square Test Statistic With Degree of Freedom 1
ORR at Day 28	Interim Analysis 1	112 (25.7)	–	–	–	–
	Interim Analysis 2	360 (82.6)	0.0122/0.0122	2.249810	0.0122305	5.061645
	Final	436 (100)	0.0128/0.025	2.015483	0.02192703	4.062172

If, at Interim Analysis 2, the observed number of subjects who have completed Day 28 is different from 360, then the boundaries for efficacy in [Table 2](#) will be recalculated using observed information fraction.

The interim analyses will be performed by an independent statistician and programmer not involved with the conduct of the study as described in the DMC charter.

At the Interim Analysis 2 clinical data cutoff date, the date when the 240th eligible subject randomized in the study has reached Day 180, 360 subjects are expected to have been randomized. Testing of Day 28 ORR will be conducted for subjects who have completed the Day 28 visit or withdrew from the study by the clinical data cutoff date. This means that subjects who were ongoing but had not yet reached the Day 28 visit by the Interim Analysis 2 clinical data cutoff date will be excluded from both the Day 28 ORR and NRM efficacy analyses.

[Figure 4](#) depicts the recommended decision process at Interim Analysis 2: first, testing Day 28 ORR using stratified CMH and assuming 360 subjects have completed Day 28 or withdrew from the study by the cutoff date, if observed normalized test statistic is ≤ 1.46 , it is recommended to stop the study for futility; if the observed normalized test statistic of Day 28 ORR is ≥ 2.25 , then the NRM rate at Day 180 will be tested using the Bonferroni method. If both the primary efficacy analysis and the key secondary efficacy analysis pass their corresponding efficacy boundary, the superiority of itacitinib over placebo for both the Day 28 ORR and Day 180 NRM endpoints can be claimed at Interim Analysis 2.

Table 3: Schedule of Assessments

Visit Day Item	Screening -28 to -1	Treatment ^a												EOT ^d	Retreatment ^e	Follow-Up		
		D1	D7	D14	D21	D28	D35	D42	D49	D56 ^b	D100	D180	D365 ^c			Safety ^f	GVHD ^g	Survival ^h
Informed consent	X																	
I/E criteria	X	X																

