9. INTERIM ANALYSES AND FINAL ANALYSES

9.1. Overview of Interim Analyses

There are 2 planned interim analyses. The first interim analysis is for futility checking and second interim analysis is for efficacy and futility.

9.1.1. Interim Analysis 1

The first interim analysis for futility only will be performed when 112 (25.7% of the planned 436 subjects) have completed the Day 28 visit or withdrew early from study. No alpha will be spent during the first interim analysis. The stopping rule is nonbinding. When the conditional power is < 20%, the sponsor may consider terminating the trial if the totality of evidence is warranted.

Interim Analysis 1 on ORR at Day 28 will be carried out as follows:

F1: Obtain CMH test statistic (chi-square test with degree of freedom 1);

F2: Obtain observed normalized test statistic z by taking square root of CMH in F1;

F3: Calculate conditional power based on $\Phi\left(\frac{z}{\sqrt{t(1-t)}} - \frac{z_{\alpha/2}}{\sqrt{1-t}}\right)$ (Jennison and Turnbull 1999),

where Φ is the cumulative distribution function of the observed normalized test statistic z . t is the information fraction and (ie, observed sample at interim divided by planned total sample size 436); $t = 0.257$ at Interim 1 and $z_{\alpha/2} = 1.96$.

F4: If conditional power is less than 20%, the sponsor may consider stopping the study for futility; otherwise, the study will continue.

9.1.2. Interim Analysis 2

For Interim Analysis 2, the analysis of both efficacy and futility will use a clinical database cutoff based on when 240 eligible subjects (55.0% of the targeted 436 subjects) have completed the Day 180 visit or withdrawn from the study prior to Day 180.

The Hwang-Shih-DeCani alpha spending function with shape parameter -4 (O'Brien Fleming like boundary) will be used to define nonbinding upper efficacy boundary for the primary analysis of ORR at Day 28 when approximately 240 eligible subjects reach Day 180. Based on enrollment projection, there will be approximately 360 subjects who have completed Day 28.

The futility analysis based on test of ORR at Day 28 at Interim Analysis 2 will be carried out the same way as in Interim Analysis 1 (Steps F1-F4) but using the observed information fraction and observed normalized test statistic from Interim Analysis 2.

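### At Interim 2, conditional power is computed against 1.96 although the final ORR test must exceed about 2.02, so the nominal 20% futility rule is really about 16.5% at 360 subjects and lower at the sizes in Appendix D

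*SAP*

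**What the plan says.** SAP section 3.4 sets out the futility rule for Day 28 ORR. For Interim 1 it gives a "futility boundary of 0.626 as depicted in Figure 3 (equivalently conditional power equal to 0.2"). For Interim 2, in the 360-subject illustration, it gives a "futility boundary of 1.46 corresponding to conditional power of 0.2", and the next sentence reads "Critical value at final analysis is 2.02". Section 3.4.2 turns 1.46 into an instruction: at or below that value "it is recommended to stop the study for futility".

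Section 3.4.1 defines conditional power as Φ(z/√(t(1−t)) − z_α/2/√(1−t)), with z_α/2 set to 1.96. It adds: "The conditional power is calculated assuming that the estimated treatment effect at the interim analysis is the true effect". Section 9.1.1, step F3, repeats the formula and the 1.96, and Protocol section 9.2.1 has the same definition. For Interim 2, SAP section 9.1.2 says the futility analysis "will be carried out the same way as in Interim Analysis 1 (Steps F1-F4) but using the observed information fraction" and the observed test statistic. The information fraction in the illustration is "0.826 (360 subjects complete Day 28) at Interim 2".

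SAP Table 2 gives the final critical value as 2.015483. Appendix D lists final values from 2.010698 to 2.039498 for 410 to 435 subjects at Interim 2. Sections 3.4.2, 9.1.2 and 9.2 promise to recalculate the efficacy boundaries at the observed information fraction. Nothing says that the 1.96 in the conditional power formula will change with them.

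Section 3.4.1 and step F2 define z as the square root of the CMH chi-square.

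**The concern.** Conditional power at Interim 2 is the chance, given the data so far, that the final test succeeds. Under this plan it succeeds only if the final statistic reaches the group-sequential critical value, which is above 1.96. Putting 1.96 in the formula measures the chance of clearing a bar lower than the real one. It overstates conditional power and sets the futility boundary too low.

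The 20% criterion is the only numerical futility criterion in the documents. If its stated probability is wrong, those acting on it believe a trial at the boundary has a one-in-five chance of success when the chance is smaller. The gap on the probability scale widens as Interim 2 moves later, and Appendix D tabulates only late sizes.

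The unsigned square root is a separate matter. It is never negative, so the formula as written cannot distinguish a result favouring itacitinib from an equally large one favouring placebo.

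**Working it through.** **Inputs.** Planned total 436 and 360 subjects at Interim 2 (SAP 3.4.2), so t = 360/436 = 0.8257. Final critical value 2.015483 (Table 2). Constant in the formula 1.96 (SAP 3.4.1; 9.1.1, step F3). Φ⁻¹(0.20) = −0.8416. √t = 0.9087, √(1−t) = 0.4175, √(t(1−t)) = 0.3794.

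**Formulas.** CP = Φ(z/√(t(1−t)) − c/√(1−t)). Solved for the boundary at 20%: z = √t × (c + √(1−t) × Φ⁻¹(0.20)).

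**Step 1: reproduce the plan, c = 1.96.**
- Interim 2: z = 0.9087 × (1.96 − 0.3514) = 1.4617, printed as 1.46. At 1.46, CP = Φ(3.848 − 4.695) = 19.9%.
- Interim 1, t = 112/436 = 0.2569: z = 0.6257, printed as 0.626.

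Both reproduce, so the printed boundaries do rest on 1.96.

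**Step 2: Interim 2 with the value the final test must reach, c = 2.015483.**
- At 1.46: CP = Φ(3.848 − 4.827) = 16.4%. At the unrounded 1.4617: 16.5%.
- Boundary for 20%: z = 0.9087 × (2.0155 − 0.3514) = 1.512.

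**Step 3: Appendix D sizes, each with its own final critical value.**

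| Subjects at Interim 2 | t | Final critical value | Boundary with 1.96 | CP there against the final value | Boundary for 20% |
|---|---|---|---|---|---|
| 360 (Table 2) | 0.8257 | 2.015483 | 1.46 | 16.5% | 1.51 |
| 410 | 0.9404 | 2.036718 | 1.70 | 12.4% | 1.78 |
| 420 | 0.9633 | 2.039433 | 1.77 | 10.5% | 1.84 |
| 430 | 0.9862 | 2.034627 | 1.85 | 7.0% | 1.92 |

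An independent solution of the Hwang-Shih-DeCani (−4) boundaries gives 2.2503 and 2.0154 at 360 subjects (Table 2: 2.2498 and 2.0155), so the final critical value itself is sound.

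**Step 4: Interim 1.** From Interim 1 the ORR test can succeed at either later look: 2.249810 at Interim 2 or 2.015483 at the end. On the B = z√t scale, z = 0.626 gives B = 0.3173 and an estimated drift of 0.3173/0.2569 = 1.235. Success means B(0.8257) ≥ 2.249810 × 0.9087 = 2.044, or B(1) ≥ 2.0155. Under the current trend the bivariate normal probability is 19.3%; the 20% boundary is z = 0.637. Substituting 2.0155 into the single-look formula would give 18.3% at 0.626 and a boundary of 0.654, but two-look conditional power at 0.654 is 21.1%. So 0.654 misses the 20% point by 0.017, and the plan's 0.626 by 0.011.

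**Step 5: the sign.** At Interim 1, √(t(1−t)) = 0.4369 and 1.96/√(1−t) = 2.274. A result favouring placebo with signed z = −0.7 would enter as +0.7 and return Φ(1.602 − 2.274) = 25%, above the threshold. The signed value returns Φ(−1.602 − 2.274), about 0.005%.

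**The case against.** The strongest reply is that the plan is transparent and consistent with its own formula. It prints the formula and the constant, and its boundaries follow exactly. That stands: this is not a slip in evaluating the formula. The fault is a reference value that does not match the plan's own final boundary.

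Second, SAP 3.4 says the Interim 2 and final boundaries are illustrative and that the real ones will use the observed information fraction. That is true of 1.46, but it does not cure the problem. SAP 9.1.2 updates t and z only, so the operative rule keeps 1.96 whatever the size.

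Third, the practical effect is small. The rule is nonbinding and the sponsor may weigh the totality of evidence. With an assumed pooled ORR of 0.64 (midway between 0.56 and 0.72) and 180 per arm, the standard error is √(2 × 0.64 × 0.36/180) = 0.0506. A shift of 0.05 in z is then about 0.25 percentage points of ORR, or 0.0025 × 180 = 0.45 responders in one arm. Under the null, the chance of landing between 1.46 and 1.51 is 0.7%. The current version errs toward continuing. All of this stands and limits the weight of the point.

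A reader might infer that the Interim 1 boundary of 0.626 is wrong in the same way and should be 0.654. The documents do not support that. Success from Interim 1 can also come at Interim 2, and once that route is counted 0.626 is closer to 20% than 0.654. That analysis is also past: its cutoff was 25 JUN 2018, before SAP Amendment 1.

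**Conclusion.** The point holds for Interim 2. The stated 20% is 16.4% at the printed boundary of 1.46 (16.5% unrounded), and 12.4%, 10.5% and 7.0% at 410, 420 and 430 subjects. The boundaries should be about 0.05 to 0.08 higher in z. These figures rest on the SAP's current-trend assumption, its definition of information as the fraction of 436 subjects, and its tabulated final critical values.

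Three stronger conclusions might be drawn and are not supported:
- Type I error is not affected. The futility rule is nonbinding and the efficacy boundaries do not depend on it.
- The 2.039 in Appendix D belongs to t near 0.966 and cannot be paired with 1.46, which belongs to t = 0.826.
- The Interim 1 boundary does not need correcting for this reason.

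The unsigned root is a separate and valid defect. It should be corrected on its own account and lends no weight to the 1.96 point. Overall this is a modest correction to make, because a stated decision threshold should have its stated property.

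**What to change.** 1. In SAP 3.4.2 and 9.1.2, state that at Interim 2 the 1.96 in the conditional power formula is replaced by the final critical value re-derived at the observed information fraction (Table 2 or Appendix D). Align Protocol section 9.2.2.
2. Change the illustrative Interim 2 futility boundary from 1.46 to 1.51 in SAP 3.4, 3.4.2 and Figures 3 and 4. Leave 0.626 at Interim 1 unchanged.
3. In SAP 3.4.1 and step F2, define z as the signed root of the CMH statistic, positive when itacitinib is favoured.

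The cost is SAP wording, one constant and one sign in the interim program. If the futility rule is followed, moving 1.46 to 1.51 lowers power by 0.25 to 0.28 points, assuming a drift of 3.24 to 3.33 (about 90% fixed-sample power). The sign change costs nothing. If the sponsor prefers to keep 1.96, the minimum is a sentence saying that conditional power is measured against the unadjusted value, with conditional power against the actual final boundary reported beside it.
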